**REVISION HISTORY**

Revision #	Version Date	Summary of Changes
2	10/07/2022	Adding e-consent option and study visit window periods
3	03/09/2023	Updating incentive timing and sample size
4	08/03/2023	Adding recruitment flyers and transportation assistance
5	10/06/2023	Actigraphy watch return moved to the final visit instead of the first follow up visit
6	10/27/2023	Removing BMI requirement for eligibility
7	12/11/2023	Extending the age requirement from 18-45 years to 15-45 years
8	02/01/2024	Actigraphy watch return moved to the first follow up visit instead of final visit; Adding Secure Chat on Epic as a contact method during recruitment

**Protocol Title:** Implementing and Evaluating the Effect of Personalized Pain Coaches  
After Orthopaedic Surgery for Patients with Sports Medicine Injuries to Improve  
Postoperative Outcomes

---

## 1. Study Summary

Study Title	Implementing and Evaluating the Effect of Personalized Pain Coaches After Orthopaedic Surgery for Patients with Sports Medicine Injuries to Improve Postoperative Outcomes
Study Design	Three arm randomized control trial
Primary Objective	The objective of this randomized controlled trial is to examine how the integration of a trained Life Care Specialist improves postoperative recovery related to patient-reported pain outcomes following orthopaedic injury
Secondary Objective(s)	Examine how the integration of a trained Life Care Specialist improves postoperative recovery related to opioid utilization and objective functional outcomes following orthopaedic injury
Research Intervention(s)/Interactions	The LCS will work with the patient to create a pain management plan focused on behavioral education. The LCS interventions can encompass all, but not limited to, the information included below: 

• Opioid Risk Education

• Therapeutic Intervention

• Clinical Pain Coordination

Study Population	Orthopaedic patients seen at Emory and Grady
Sample Size	150
Study Duration for individual participants	~90 days
Study Specific Abbreviations/ Definitions	LCS, Life care specialist
Funding Source (if any)	National Football League (NFL)

## 2. Objectives

**Protocol Title:** Implementing and Evaluating the Effect of Personalized Pain Coaches After Orthopaedic Surgery for Patients with Sports Medicine Injuries to Improve Postoperative Outcomes

---

The *objective* of this randomized controlled trial is to examine how the integration of a trained Life Care Specialist improves postoperative recovery related to patient-reported pain outcomes, opioid utilization, and objective functional outcomes following orthopaedic injury.

**Aim 1:** Examine differences in post-surgical patient-reported pain related outcomes and opioid utilization between participants in the intervention arms compared to those in the control arm.

*Hypothesis 1.1:* Those randomized to the intervention arms will report improved average patient-reported pain related outcomes compared to participants in the control, standard of care, arm.

*Hypothesis 1.2:* Participants in the intervention arms will have decreased utilization of opioid pain medications both in the inpatient and outpatient setting.

**Aim 2:** Compare postoperative functional outcomes among intervention and control groups during their hospitalization and postoperatively.

*Hypothesis 2:* Objective functional outcomes captured from actigraphy devices will indicate improved physical functioning among those in the intervention arms compared to participants in the control arm.

**Aim 3:** Evaluate patient-reported pain related outcomes and opioid utilization between participants randomized to the in-person intervention and the telehealth delivered intervention arms.

*Hypothesis 3:* Improvements in patient-reported outcomes and opioid utilization will be similar across study arm groups, thereby indicating the utility of delivering the intervention both in person or remotely to improve care outcomes.

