#### **10. Inclusion and Exclusion Criteria**

We will recruit 150 participants from the orthopaedic sports medicine service at Grady and Emory Healthcare for this study. Individuals between 15–45 years old, scheduled for orthopaedic surgery due to sports medicine injuries (e.g., anterior cruciate ligament tears, meniscus injury, rotator cuff injury, etc.), and those who are actively employed or full-time athletes prior to injury will be eligible. Individuals unable to provide consent, those undergoing revision procedures, individuals without access to an internet connected device, and individuals who are unemployed or retired at time of injury will be ineligible. No one will be excluded from participation based on gender, race, or ethnicity. Individuals who are incarcerated or pregnant will not be eligible. Individuals unable to consent and those unable to communicate in English will be excluded since all surveys are validated in English.

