#### **19. Data Analysis, Management and Confidentiality**

**Protocol Title:** Implementing and Evaluating the Effect of Personalized Pain Coaches After Orthopaedic Surgery for Patients with Sports Medicine Injuries to Improve Postoperative Outcomes

---

Descriptive statistics will be used to examine the sample's characteristics and demographics (e.g., means, frequencies). Paired t-tests will be used to examine changes within participants from pre- to post-surgery. Mixed effects modeling will be used to examine mean change in outcomes over time and based on demographics as well as differences between those who do and do not work with the LCs while wearable devices are collecting data. Surveys will be coded with study participant ID numbers. All hard copies will be stored in locked filing cabinets in the PI's office. Paper survey data will be entered into RedCap. A master list of study ID # and names with emails of participants will be stored on Emory servers and only accessible to the PI and the coordinator.

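### Hypothesis 3 infers that both delivery modes are useful from their similarity to each other, with no condition that either be better than control

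*Combined protocol and SAP*

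**What the plan says.** Section 2 (Objectives) sets Aim 3 as a comparison "between participants randomized to the in-person intervention and the telehealth delivered intervention arms". For patient-reported outcomes and opioid use, Hypothesis 3 then predicts that improvements "will be similar across study arm groups, thereby indicating the utility of delivering the intervention both in person or remotely to improve care outcomes".

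Comparison with control appears elsewhere in the same section. Hypothesis 1.1 states "Those randomized to the intervention arms will report improved average patient-reported pain related outcomes compared to participants in the control, standard of care, arm". Under an aim that names control as comparator, Hypothesis 1.2 states "Participants in the intervention arms will have decreased utilization of opioid pain medications both in the inpatient and outpatient setting". Neither says whether the two LCS arms are pooled or must each succeed, and Hypothesis 3 refers to neither.

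Section 19 gives no significance level, definition of similarity, margin, testing order or in-person versus virtual contrast. For change over time it says "Paired t-tests will be used to examine changes within participants from pre- to post-surgery". It also plans mixed models for mean change over time and for the difference between those who do and do not work with the LCS, the latter tied to the period of wearable data collection. Section 10 gives the size: "We will recruit 150 participants from the orthopaedic sports medicine service at Grady and Emory Healthcare for this study".

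**The concern.** The word linking the two halves of Hypothesis 3 makes similarity the ground for utility. Two modes that do nothing are also similar, so the conclusion does not follow from the premise. Interchangeability of two modes and benefit from either are different claims, and the second needs the control arm.

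The reference to improvements does not clearly supply that. Hypothesis 3 does not define improvement against control, and the paired pre/post tests in Section 19 involve no control. Patients recovering from surgery could show such change in every arm.

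At stake is the claim that remote and in-person delivery both improve care. Followed as written, Aim 3 could support it in the same trial in which Aim 1 finds no benefit.

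**Working it through.** **Inputs.** Total 150 (Section 10). The allocation ratio is not stated, so 150/3 = 50 per arm is an assumption. Alpha, margin and effect sizes are not stated either. I assume two-sided 5% tests, a normal outcome with equal SDs, and illustrative effects of 0 and 0.5 SD. Results are in SD units. The plan has no figure of its own to reproduce.

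**1. Similarity as a non-significant difference, one outcome.** If the modes are truly equal, P(p > 0.05) = 1 − 0.05 = 95%. This depends on neither sample size nor the common effect of the two modes, so it is 95% when both effects are 0 and 95% when both are 0.5 SD. At alpha 0.10 it is 90%, and at 0.01 it is 99%.

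**2. Several outcomes, all required to be non-significant.** For k independent outcomes the probability under no effect is 0.95^k:
- k = 2: 90%
- k = 4: 81%
- k = 6: 74%

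At a correlation of 0.5, simulation gives 91%, 85% and 79%. The range is about 74% to 91%.

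**3. Similarity as an equivalence test** (two one-sided 5% tests, margin M). The standard error of the difference is SD × √(2/50) = 0.2 SD. With equal modes, P(pass) ≈ 2Φ(M/0.2 − 1.645) − 1, or 0 where M/0.2 is below 1.645:
- M = 0.3: 1.5 − 1.645 < 0, so about 0%
- M = 0.4: 2Φ(0.355) − 1 = 28%
- M = 0.5: 2Φ(0.855) − 1 = 61%
- M = 0.6: 2Φ(1.355) − 1 = 82%

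Simulation with t tests gives 0.4%, 27%, 60% and 82%. These figures also depend only on the difference between the modes. A margin therefore defines similarity but does not bring control into the inference.

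**4. Adding a condition against control** (simulation, 50 per arm, similarity read as p > 0.05, superiority at two-sided 5%):

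| Utility is claimed if | Neither works | Both work, 0.5 SD | One works 0.5 SD, other 0 |
|---|---|---|---|
| Modes similar | 95% | 95% | about 30% |
| Similar, and pooled LCS beats control | 2.4% | 78% | about 9% |
| Similar, and each arm beats control | 0.5% | 54% | about 2% |

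The first row is the criterion as written, under this reading. It gives the same answer in the first two columns, which are the two cases it has to separate. With a 0.5-SD equivalence margin in place of p > 0.05, the each-arm condition passes about 0.4% of the time under no effect.

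**The case against.** The strongest defence is that Hypothesis 3 is a prediction, not a decision rule, and that it speaks of improvements. Hypotheses 1.1 and 2 use the same idea explicitly against control, so Hypothesis 3 can be read as taking up those improvements and asking whether they hold in both modes. The primary objective and Aims 1 and 2 are comparisons with control in the same trial, so a failed programme would be visible. Pre/post recovery is also a weaker explanation for opioid use: Section 6 describes operating-room, inpatient and postoperative opioid doses and names no preoperative baseline.

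Much of this stands. It limits the harm to one unwritten link in a later aim. It also means that a calculation with two equally harmful modes would test a rule from which the word improvements has been removed, so I do not rely on one. It does not supply the link: no sentence makes the utility conclusion conditional on a result against control, and for patient-reported outcomes the named change analysis could be satisfied by recovery.

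Three stronger readings are tempting and should be resisted.

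- A reader might infer that an ineffective programme would pass 95% of the time under this plan. That figure is 1 minus an assumed alpha, for one outcome, under a rule the plan never states.
- A reader might infer that a margin test favours ineffective programmes. It does not: its pass rate is the same when both modes work equally. The fault is failure to discriminate, not bias.
- A reader might take the reference to study arm groups as including control, so that Hypothesis 3 would be met when the LCS does nothing. Aim 3, directly above, limits the comparison to the two LCS arms.

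**Conclusion.** The concern holds as a flaw in the stated inference. Similarity between the two LCS arms cannot by itself show that either improves care, and the documents do not make the conclusion wait for a result against control. This is separate from the missing definition of similarity, because an equivalence margin alone would leave it in place.

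The size cannot be given as one number. Under no effect, with 50 per arm assumed, the criterion is met about 95% of the time for one outcome judged by p > 0.05, about 74% to 91% if two to six outcomes must all be non-significant, and about 0% to 82% under equivalence margins of 0.3 to 0.6 SD. The structural point does not depend on which applies. The documents do not support a claim that the trial would hide a failed programme, since Aim 1 would show it. The wording should be corrected; the design need not change.

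**What to change.** In Hypothesis 3, replace the closing reference to study arm groups with *between the in-person and virtual LCS arms*. Add to Section 19:

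*A statement of utility for both delivery modes on an outcome will be made only if each LCS arm is superior to control on that outcome; otherwise the in-person versus virtual result will be reported as a difference with its 95% CI, beside each arm's difference from control with its 95% CI, with no claim of utility.*

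The significance level for superiority should be stated with it, since Section 19 gives none. How similarity is judged still has to be defined separately; the condition can be used with either reading above.

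The each-arm condition is proposed because the claim concerns both modes. A pooled LCS-versus-control condition costs less power (78% against 54% when both modes work by 0.5 SD), but it still passes about 9% of the time when only one mode works. It is acceptable only for a statement about the programme overall.

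The change needs no new patients, data or procedures. Its cost is that utility becomes harder to claim: from 95% to about 54% when both modes truly work by 0.5 SD, under the p > 0.05 reading.

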### **3. Background**

Longitudinal analyses indicate that both greater pain severity and duration precede poor functioning and prolonged opioid use.(Althaus et al., 2014; Kent et al., 2021) This finding suggests that optimizing pain management, soon after painful events, such as orthopaedic injury, is vital to reducing risks related to prolonged opioid use. However, opioid dominant pain management, which remains the standard of care across many health systems and in orthopaedic surgery, elevates the risks for ineffective pain management and, subsequently, opioid dependency by only targeting a select number of pain receptors.(Bedard et al., 2018; Hadlandsmyth et al., 2018) Multimodal analgesia, which combines analgesic drugs from different classes and employs analgesic techniques that target multiple pain-related receptors, is recommended in the treatment of acute postoperative pain because its synergistic effect maximizes pain

**Protocol Title:** Implementing and Evaluating the Effect of Personalized Pain Coaches After Orthopaedic Surgery for Patients with Sports Medicine Injuries to Improve Postoperative Outcomes

---

relief at lower analgesic doses, thereby reducing the risk of adverse opioid-related effects and chronic pain.(Polomano et al., 2017) Multimodal analgesia includes the use of nonpharmacological pain management approaches. Patients can implement nonpharmacological pain management techniques themselves, or ideally work with clinical team members to be educated on and implement them, as part of multimodal opioid-sparing postoperative pain management. However, limited access to non-pharmacologic pain services is associated with initiating opioid prescriptions and persistent pain.(Karmali et al., 2021) Therefore, patients without access to and training on evidence-based non-pharmacological pain management approaches face higher risks of receiving opioid dominant pain management. Novel approaches are needed to expand patients access to and understanding of multimodal pain management approaches after sustaining sports medicine related injuries.

Our interdisciplinary team has developed and tested a novel clinical care team role focused on optimizing pain management after surgery, known as a Life Care Specialist. Life Care Specialists provide patient-centered pain management care coordination, teach patients how to implement non-pharmacological pain management approaches, and deliver opioid safety focused pain education, not only during acute hospitalization but also throughout postoperative recovery. All Life Care Specialists have advanced degrees and are certified to provide patients with non-pharmacologic pain management strategies, including progressive muscle relaxation, music therapy, diaphragmatic breathing, aroma therapy, and also assist patients with implementing best practices to promote sleep hygiene to enable restful restorative sleep after surgery. Life Care Specialists provide pain focused care coordination for patients with complex needs after orthopedic injury, including communicating patient care needs and goals of care to clinical care team members (e.g. surgeons, acute pain service, physical therapy, nursing staff), connecting patients to yoga instructors, massage therapists, and engaging behavioral health consults to work with patients over time to improve biopsychosocial pain presentations. The role of the Life Care Specialist was based on success seen in introducing paraprofessionals and peer navigators into other clinical practice settings. For example, in pediatric settings there is significant evidence showing that non-pharmacological interventions delivered by Certified Child Life Specialists leads to more cooperation, reduction in perceived pain, and higher satisfaction scores from patients and their families.(Bandstra et al., 2008; Sanchez Cristal et al., 2018) Patients navigators have been shown to improve care outcomes and pain for patients with numerous chronic conditions.(Macdonald et al., 2017; Natale-Pereira et al., 2011) Similar to these other paraprofessional roles, Life Care Specialist help to improve postoperative care outcomes by leveraging their specialized training to implement systematic biopsychosocial pain assessments as well as increase access to and providing care coordination for utilizing non-pharmacological pain management approaches. The Life

Care Specialist serves as a point of contact to curate the often-disjointed care patients face during their postoperative recovery and when accessing non-pharmacological approaches.

#### **4. Study Endpoints**

During the conduct of this study, assessments will occur one month to one week prior to surgery, 2 weeks, 6 weeks, and 3 months postoperatively. Study measures at these points will assess patient-reported outcomes using surveys, opioid consumption using both electronic health records and remote monitoring, and functioning using wearable actigraphy devices.

#### **5. Study Intervention/Design**

Patients will be randomized to either:

- (1) In person LCS intervention** - With *Opioid Risk Education*, patients will receive opioid education after completing the validated Opioid Risk Tool (ORT), a detailed substance abuse survey and mental health screening, and Naloxone education. *Therapeutic Intervention* will include the Community Resiliency Model (CRM). *Clinical Pain Coordination* will include directed referrals for complex needs, including mental health and substance use disorders, as needed. In addition to above mentioned 3 intervention components, all patients in the LCS intervention arm will also receive the current standard-of-care. The Community Resiliency Model (CRM) is a noncognitive variant of mindfulness, emphasizing attunement to interoceptive and exteroceptive signaling cues for regulation of autonomic responses to stress (Grabbe, Higgins, Baird, Craven & San Fratello, 2020). CRM was derived from somatic psychotherapy and self-stabilization interventions using body sensation awareness. Body sensation awareness is called introspection and is a key component of mindfulness. Awareness of internal body sensation occurs in the insular cortex and adjacent brain structures, which serve as cerebral centers regulating emotional regulation, empathy, and social interaction (Simmons et al., 2013). Implementing these techniques may preventatively attenuate the immediate impact of stressors. For example, the CRM model has been implemented across several settings and populations and has been associated with improved well-being, resiliency, and physical symptoms (Grabbe et al., 2020; Grabbe et al., 2021; Habimana et al., 2021). CRM skills are introduced over a sixty-to-ninety-minute session, allowing for a brief introduction and application of skills by participants.

- (2) **Virtual LCS intervention** - With *Opioid Risk Education*, patients will receive opioid education after completing the validated Opioid Risk Tool (ORT), a detailed substance abuse survey and mental health screening, and Naloxone education. *Therapeutic Intervention* will include the Community Resiliency Model CRM).. *Clinical Pain Coordination* will include directed referrals for complex needs, including mental health and substance use disorders, as needed. In addition to above mentioned 3 intervention components, all patients in the LCS intervention arm will also receive the current standard-of-care.
- (3) **No LCS intervention** - Patients will receive the current standard-of-care for pain management in the aftermath of surgery, which includes: a standardized prescription protocol, hospital-system approved discharge instructions which provide written instruction on how to taper opioid use, links to written/online resources for opioid misuse, overdose prevention, and State-approved disposal options.

## **6. Procedures Involved**

If the patient meets inclusion criteria, the CRC will visit patient during their preoperative consult or call the referred patient through his/her number listed on Epic. If unable to visit in person and reach through call, the CRC will message patient through the Secure Chat feature on Epic to potentially schedule an e-consent. If informed consent is obtained, they will be enrolled into REDCap for randomization into one of the three groups. A simple number generator, within RedCap, will sequentially randomize participants into control or one of the two intervention arms. After consenting, enrolling, and allocation, research staff will administer a battery of measures on tablets stored in REDCap, or on paper and later transcribed into REDCap to all participants. In the event the participant is unable to complete study measures during the clinic visit they will be emailed a secure link to RedCap to complete the consent form and the study measures.

Those randomized to the intervention will either meet with a Life Care Specialist for 1 hour before surgery, either in person or via Zoom® during their preoperative consult or at another time no later than 24 hours before surgery.

During their follow up visits with the surgical team at Grady Hospital or Emory Orthopaedics scheduled at 2-weeks, 6-weeks, and 3-months postoperatively participants will again be provided a tablet to complete outcome measures. In the event participants cannot physically travel to the clinic, appointments will be conducted over video conferencing and participants will have the option to be emailed the outcome measures to complete. If they are unable to complete the measures via email within 72-hours study staff will call participants to complete measures over the phone. If no response, paper copies of the measures will be mailed to participants with prepaid

**Protocol Title:** Implementing and Evaluating the Effect of Personalized Pain Coaches After Orthopaedic Surgery for Patients with Sports Medicine Injuries to Improve Postoperative Outcomes

---

postage to return them or QR code post cards to complete surveys. There is a one week window for the first follow up visit, two week window to complete measures for the second follow up study visit, and four weeks for the last study visit. Study staff will call participants and offer to video conference with them within 48 hours of surgery to review how to wear the actigraphy device and use the MEMS cap.

The following data will be collected on the patients:

- Demographics: Name, date of birth, date of admission, gender, ethnicity, body mass index, zip code, insurance
- Health record data: Data abstraction from health records include injury severity score, mechanism, drug screen on arrival, alcohol screen, pre-existing conditions, inpatient complications, surgical time, regional anesthesia, medication received, and opioid medication doses discharged with.
- Comprehensive social determinants of health (SDOH) survey: This measure includes assessments of housing, financial stability, education, community context, intimate partner violence, health literacy, prior personal and family substance use, a validated measure of post-traumatic stress disorder, adverse childhood experiences, and mental illness. This has been utilized in prior research by this team and takes approximately 20-25 minutes to complete.
- Revised Opioid Risk Tool (ORT): The ORT is a self-reported measure used to ascertain a participant's current and future risk of aberrant drug-related behaviors in patients prescribed opioid therapy.(Cheatle et al., 2019; Webster & Webster, 2005) Recently a shortened revised ORT was recently developed and will be used in this study.(Cheatle et al., 2019) Across 9-items, this tool assesses family history of substance abuse, personal history of substance abuse, age range, and current psychological disease. Each endorsement is scored as 1 for a total score ranging from 0 to 9. Scores of 3 or greater are predictive of high risk for opioid use disorder.
- PTSD screener: This screener is a 5-item screening tool used to assess previous exposure to traumatic events and subsequent presence of the DSM-V diagnostic criteria for PTSD.(Prins et al., 2016) Each item respondents report "Yes" to can be scored as a point so that a minimum of 3 points is used in primary care settings to be considered probable PTSD.
- Sleep Disturbance, Physical Function, Pain Interference, Prescription Pain Medication Misuse: The *PROMIS Sleep Disturbance* examines respondent's global severity of insomnia, sleep disruption, and sleep quality over the past seven days. This PROMIS scale is more sensitive at detecting sleep problems than historical measures, such as the Pittsburgh Sleep Quality Index.(Yu et al., 2012) Again, each of the 4 Likert scale items' raw score are converted to t-scores, ranging from 0 to 100. Like all PROMIS measures, t-scores are normed to the US population, with a mean of 50 and standard deviation of 10.(Cook et al., 2014) Lower scores indicate better sleep. *PROMIS Physical Function* measures participants' self-reported capability to conduct physical activity. This includes capturing function in upper extremities and

lower extremities (walking or mobility) as well as a respondent's ability to conduct activities of daily living. There are 4-items on the short form questionnaire and respondents report their capabilities to perform each task on a Likert scale from 5, "without any difficulty", to 1, "unable to do". All 4-items' raw scores are summed before being transformed into t-scores ranging from 0 to 100. Higher scores are better and indicate greater physical function. The validated instrument is comparable to numerous legacy measures often used across diverse patient populations. (Jensen et al., 2015; Schalet et al., 2016) *The PROMIS Pain Interference* scale assesses the extent to which pain impedes engagement with social, cognitive, emotional, physical, and recreational activities over the past 7 days. Pain interference is an essential aspect of pain management to capture in order to better understand how pain impacts the activities of individuals rather than subjective severity alone. On each of the scale's 4-items respondents choose how much pain impeded a specific function or activity, ranging from 1, "not at all", to 5, "very much". Scores are summed across all items and transformed to a t-score ranging from 0 to 100, with lower t-scores indicate less interference due to pain. The *PROMIS Pain Interference* scale has been found to be comparable in responsiveness to traditional measures of pain interference used including the Brief Pain Inventory Interference subscale and the 36-Item Short Form Survey (SF-36) Bodily Pain scale. (Askew et al., 2016; Chen et al., 2019; Raichle et al., 2006; Stone et al., 2016) *The PROMIS measure of Prescription Pain Medication Misuse* assesses current abuse of prescription pain medication, chiefly opioids. The scale has been validated in patient populations with chronic non-cancer pain and has been found to be highly correlated with the Pain Medication Questionnaire (PMQ)."

- Naloxone Questionnaire: Each participant will complete a Naloxone questionnaire evaluating knowledge and details of utilization, if applicable, and signs and symptoms of an overdose. The Opioid Overdose Knowledge Scale is a validated instrument where higher scores indicate greater understanding.
- Opioid utilization: Inpatient and operating room opioid utilization will be extracted from the electronic health record (EHR) by study staff upon participants' discharge from the hospital. Opioid medication dosage will be transformed to a total universal measure known as morphine milligram equivalent (MME). MME will be averaged over the length-of-stay (LOS) for a daily dosage, known as MME/day. Additionally, the study team will review participants' EHR at each study time point up to 3-months to determine MME throughout postoperative recovery and rehabilitation. Medication Electronic Monitoring (MEMS) devices will be used to assess medication utilization and adherence rates. They are Bluetooth enabled caps that fit on standard medicine bottles and record participants' medication utilization. Participants will be dispensed their opioid medication by the pharmacy in the MEMS equipped containers and informed to return their bottle at their next follow up visit.
- Pain numerical rating scale (NRS): The NRS requires respondents to rate the intensity of their pain on a defined scale from 0, "no pain", to 10, "the worst pain imaginable". The NRS is a commonly used pain assessment tool in both clinical practice and

research. (Farrar et al., 2010) However, the NRS is a single static measure of pain and does not capture the biopsychosocial presentations of pain including physical functioning. As such a battery of objective (e.g. actigraphy) and patient-reported outcomes are needed to best ascertain patient participants' pain experiences. Inpatient NRS, which is recorded by the clinical care team throughout each day, will be extracted from the electronic health record (EHR) by study staff upon participants' discharge from the hospital.

- Mindful Attention Awareness Scale: The MAAS is a validated 15-item scale designed to assess a core characteristic of dispositional mindfulness, namely, open or receptive awareness of and attention to what is taking place in the present.
- Actigraphy based sleep and activity data (e.g. average hours of sleep, average daily steps): Study participants will be provided with a wrist actigraphy device to wear during a week before their hospitalization and throughout their recovery until their 2-week follow up appointment with the surgical team or until the watch battery loses its charge, whichever occurs first. Participants will return their actigraphy devices at the 2-week follow up appointment or be provided a pre-paid envelope to take home and mail back the device after the visit. Wrist actigraphy is a valid and objective tool to measure activity patterns and sleep-related parameters, which has been used in patient populations with both acute and chronic pain.(An et al., 2020; Smith et al., 2018) Actigraphy data includes objective quantitative measures of sleep, such as total sleep time, sleep latency, fragmentation, wake after sleep onset, and sleep efficiency. Additionally, activity level is also captured using wrist actigraphy, including total activity time, steps, physical activity intensity, and total energy expenditure. Participants will receive, and be trained on how to wear, a screen-less actigraphy device on their wrist (GT3XP-BTLE, Actigraph, LLC, USA). Devices will be set to record in 30-second epochs at a medium sensitivity level for scoring sleep and wake time. Wear time validation will be accomplished using the Choi algorithm, as it more accurately estimates time worn accounting for forward and backward motions.(Choi et al., 2011) The sleep data will be computed using the Cole-Kripke algorithm, which accurately distinguishes sleep from wakefulness approximately 88% of the time.(Cole et al., 1992) Metabolic equivalent of tasks and energy expenditure will be measured with the Freedson algorithms.(Freedson et al., 1998) By uniquely pairing actigraphy data with PROMIS patient-reported pain, sleep, and physical function measures, this study will be one of the first to provide a robust analysis of sleep quality and activity in tandem to pain presentations in adult surgical patient populations during hospitalization and throughout immediate post-discharge recovery following surgery. These research efforts adhere to recommended best practices for using actigraphy to examine health outcomes.(Berger et al., 2008)
- Field notes and participant quotes: Field notes are widely recommended in research as a means of documenting needed contextual information and accurately capturing participants' statements in real time. As such study staff will transcribe notes on their encounters with research participants, including summary of interaction and representative quotes from participants.

The LCS will work with the patient to create a pain management plan focused on behavioral education. The LCS interventions can encompass all, but not limited to, the information included below:

- *Opioid Risk Education*
  - Patients will be provided with education about substance misuse and the opioid epidemic
  - Patients will be educated by the LCS on safe methods for disposal of unused pain medications
- *Therapeutic Intervention*
  - The Community Resiliency Model skills
    - Tracking
    - Resourcing
    - Grounding
    - Gesturing
    - Shift and Stay
    - Help Now!
- *Clinical Pain Coordination*
  - The LCS team will work closely with the [name] as well as pain specialists [name], Co-Director of the acute pain service at Grady and [name], Director of the Medication Assisted Opioid Therapy Clinic.
  - LCS will complete the Behavioral pain assessment tool. The Checklist of Nonverbal Pain Indicators (CNPI) is a quick behavioral assessment used by clinicians to assess nonverbal indicators of potential pain patients are in such as grimacing, bracing, rubbing, and restlessness at rest and when moving.

